date (i.e., similar to the matched oxygen therapy patient in time from the fibrosing ILD diagnosis date to the index date, and during the same continuous enrollment period as the fibrosing ILD diagnosis date).

NOTE: Following review of results from Aim 1, the study team will determine whether continuous enrollment criteria for Aim 2 and Further Aim requires revision.

Variables:	
Aim 1
 
Outcomes: time to initiation of oxygen therapy; time to sustained oxygen therapy use; sustained oxygen therapy use within the first 12 months of follow-up
 
Baseline covariates: demographic characteristics (age, sex, race/ethnicity, geographic region, insurance type, index year), clinical characteristics (underlying ILD type; respiratory diseases; other clinical characteristics; Quan-Charlson comorbidity score; Agency for Health Research and Quality [AHRQ] comorbid conditions; smoking; pulmonary rehabilitation) healthcare utilization characteristics (provider specialty; medication use; all-cause HCRU; all-cause health care costs)
 
Stratification: IPF vs non-IPF ILD
 
Aim 2 [REDACTED]
 
Exposure: oxygen therapy vs no oxygen therapy
 
Primary Outcomes: Time to disease progression; time to all-cause mortality; time to hypoxemia, time to acute exacerbations, counts of acute exacerbations
 
[REDACTED]
 
Baseline covariates: demographic characteristics (index year, age, sex, race/ethnicity, geographic region, insurance type), clinical characteristics (underlying ILD type; respiratory diseases; other clinical characteristics; Quan-Charlson comorbidity score; AHRQ comorbid conditions; smoking; pulmonary rehabilitation) healthcare utilization characteristics (provider specialty; medication use; all-cause HCRU; all-cause health care costs)

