7.3 VARIABLES

Variables related to the study period will be defined as follows:

Aim 1

- **Fibrosing ILD diagnosis date**—The first ILD diagnosis date for patients with ≥ 2 fibrosing ILD diagnoses on different dates and within 365 days. The fibrosing ILD diagnosis date is the first day of follow-up observation time for Aim 1.
- **Pre-ILD baseline period**—The 12-month period prior to the fibrosing ILD diagnosis date.
- **Aim 1 follow-up period**—The variable period starting on the fibrosing ILD diagnosis date and continuing until the earliest of the following: disenrollment from the health plan, death, or end of the study period. The Aim 1 follow-up period will be used to assess Aim 1 outcomes.
 - **All-cause mortality**—Death will be used as a censoring event and is further defined in Section 7.3.3.1.

Aim 2

- **Index date**—For the oxygen therapy cohort, the first date following the fibrosing ILD diagnosis date with a claim with diagnosis for oxygen therapy; for the no oxygen therapy cohort, a date within the same continuous enrollment period as the fibrosing ILD diagnosis date that is similar to the matched oxygen therapy patient in time from fibrosing ILD to index date. The index date is the first day of follow-up observation time for Aim 2 and Further Aim.
- **Pre-index baseline period**—The 12-month period prior to the index date.
- **Aim 2 follow-up period**—The variable period starting on the index date until the earliest of the following: disenrollment from the health plan, death, or the end of the study period. Matched pairs will be given the same duration of follow-up. The Aim 2 follow-up period will be used to assess Aim 2 and Further Aim outcomes.
 - **All-cause mortality**—Death will be used as a censoring event and is further defined in Section 7.3.3.1.

An overview of the analytic study variables and the study periods for which each analytic variable will be reported is provided in Table 1. Additional variable information is provided in Sections 7.3.1 to 7.3.4.

Table 1. Analytic Variables by Data Source and Time Period

Characteristic	Data source		Aim 1 time period		Aim 2 time period	
	Claims*	EHR	Pre-ILD baseline	Follow-up	Pre-index baseline	Follow-up
Aim 1 outcomes						
Oxygen therapy (time to initiation, sustained oxygen therapy use)		X		X	X	
Aim 2 outcomes						
Disease progression	X	X				X
All-cause mortality	X					X
Hypoxemia	X	X	X		X	X
Acute exacerbations	X	X				X
Patient characteristics†						
Index year	X		X		X	

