7.3.3 Aim 2 Outcomes

7.3.3.1 Primary Outcomes

All primary outcomes will be measured in the Aim 2 and Further Aim follow-up period, unless specified otherwise.

- **Time to disease progression**—Pulmonary function test (PFT) results will be captured as available in the database in the pre-ILD baseline, pre-index baseline, and Aim 2 follow-up periods among the subset of patients who have EHR data during the same

time of ILD diagnosis and oxygen therapy. All valid result values will be captured. Values closest to the fibrosing ILD diagnosis date will be reported for the pre-ILD baseline period; values closest to the index date will be reported for the pre-index baseline period; the latest values prior to the end of follow-up will be reported for the Aim 2 follow-up period. PFT tests may potentially include forced expiratory volume in 1 second (FEV₁), forced vital capacity (FVC), FEV₁/FVC ratio, lung volumes, and diffusing capacity for carbon monoxide (DLCO), as available.

Among patients or matched pairs with FVC results in the pre-index and follow-up periods, disease progression will be defined as a 10% relative change between the pre-index value and the follow-up value. Time to disease progression will be reported. Additionally, time in days from pre-index FVC result to the index date and from index date to follow-up FVC result will be reported.

- **Time to all-cause mortality**—We will assign the date of death as the 15th day in the month of death. Time to all-cause mortality will be calculated as time between index date and mortality date.

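### Time to disease progression is restricted to patients or pairs with a follow-up FVC, so death, disenrollment or lack of testing after index decides who enters a primary outcome

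*Combined protocol and SAP*

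**What the plan says.** The abstract (2.1.1) lists the outcome first among those for Aim 2: "Primary Outcomes: Time to disease progression; time to all-cause mortality". Section 7.3.3.1 also places it under primary outcomes.

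The same section sets three conditions that matter here:
- Source of the data: "Pulmonary function test (PFT) results will be captured as available in the database". No test schedule is given.
- Who is analysed: "Among patients or matched pairs with FVC results in the pre-index and follow-up periods".
- The event: "disease progression will be defined as a 10% relative change between the pre-index value and the follow-up value". On which follow-up result is used, "the latest values prior to the end of follow-up will be reported for the Aim 2 follow-up period".

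Section 7.3 ends Aim 2 follow-up at disenrollment, death or study end, whichever comes first. It adds "Matched pairs will be given the same duration of follow-up" and, on mortality, "Death will be used as a censoring event and is further defined in Section 7.3.3.1".

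The only visible wording on competing events is in 7.6.1.2. It is optional and concerns oxygen initiation in Aim 1. Section 7.8 notes that the analysis depends on valid EHR values being available, but does not mention selection by survival or by retention to a repeat test.

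**The concern.** Matching balances the cohorts at the index date. The progression analysis then keeps only those who later had an FVC. A patient who worsens and dies before the next test cannot meet that condition. Section 7.3 makes death a censoring event, but censoring applies to people already in the risk set, and 7.3.3.1 has no rule that puts this patient there. Patients who leave the plan, or stay enrolled but are never retested, are lost in the same way.

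The wording also leaves open whether the restriction applies to patients or to pairs. On the second reading, one untested member removes both.

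The patients most likely to be lost to death are those declining fastest. If oxygen users and non-users differ in mortality or in how often they are tested, the two cohorts lose different fractions of their worst patients. Mortality is itself a primary question, so equal mortality cannot be assumed. The progression result would then partly reflect who survived to be retested.

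**Working it through.** **The plan's own figures.** There are none to reproduce. The documents give no death, disenrollment, testing or progression rate for this outcome, and section 7.5 holds feasibility counts only. Every rate below is an assumption.

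**Step 1: share with no repeat FVC, closed form.** With constant yearly rates of death d, disenrollment l and testing t, the share removed is (d + l)/(d + l + t). Take l = 0.2:
- d = 0.1, t = 2: 0.3/2.3 = 13%
- d = 0.2, t = 1: 0.4/1.4 = 29%
- d = 0.4, t = 0.5: 0.6/1.1 = 55%

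**Step 2: share removed, by simulation (400,000 patients per scenario).** Assumptions: progression hazard 0.4/year; death hazard 0.15 or 0.30/year, tripled after progression; disenrollment 0.25/year with a 3-year cap; first repeat FVC uniform on 0.5 to 1.5 times a mean gap of 6 or 12 months. For pairs, follow-up is taken to stop at the first death or exit of either member. This is an assumption, since section 7.3 says the durations are equal but not how they are set.

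| Mean gap, base death hazard | Died before repeat FVC | Left before it | Patients retained | Pairs with both retained |
|---|---|---|---|---|
| 6 months, 0.15 | 8% | 11% | 81% | 61% |
| 6 months, 0.30 | 15% | 11% | 74% | 50% |
| 12 months, 0.15 | 16% | 20% | 64% | 35–36% |
| 12 months, 0.30 | 28% | 18% | 54% | 23% |

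So 100 − 81 = 19% to 100 − 54 = 46% of patients have no repeat FVC before death or exit. Squaring patient retention would give 55–65% and 29–41% of pairs, but that ignores the common follow-up.

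The closed form for pairs shows the same kind of loss. Let r be the summed exit rates of both members. The share of pairs kept is [2t/(2t + r)] × [t/(t + r)]. With t = 1 and r = 0.2 + 0.1 + 0.4 = 0.7, this is 0.741 × 0.588 = 44%. With r = 0.4 + 0.2 + 0.4 = 1.0, it is 0.667 × 0.5 = 33%.

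**Step 3: effect on the comparison.** Keep the step 2 model, let tests continue at the same gap, date progression at the first test that shows it, give oxygen a mortality hazard ratio of 1.5, and give it no effect on progression. At base hazard 0.30, death before a repeat FVC removes 21% (oxygen) against 15% (control) with the 6-month gap, and 38% against 28% with the 12-month gap. The oxygen/control progression rate ratios, in the row order of the table, are:
- Censoring at last FVC, both-values set: 0.97, 0.94, 0.95, 0.91.
- Censoring at last FVC, all patients (untested ones censored at index): the same four values.
- Censoring at end of follow-up, both-values set: 0.96, 0.92, 0.93–0.94, 0.89.
- Censoring at end of follow-up, all patients: 0.95, 0.90, 0.90, 0.82.

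The second line must equal the first: a patient censored at time zero adds no event and no person-time. In the fourth line, widening the set moves the ratio further from 1.

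**Step 4: a second model.** Here death and progression share a lognormal frailty, testing is 1/year, exit 0.2/year, control death 0.15/year, progression 0.3/year, the limit is 3 years, and the latest FVC is used.
- Equal mortality: 26% removed in each cohort, ratio about 1.0.
- Death hazard ratio 2, no progression effect: 32% against 26% removed. The ratio is 0.94 in the both-values set, 0.95 for progression fully observed in everyone while alive, and 1.26 for progression or death in everyone.
- Death hazard ratio 2, progression hazard ratio 1.5: 1.25, 1.36 and 1.51 respectively.

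The step from 0.94 to 1.26 is mostly a change of estimand. The step from 1.36 to 1.25 reflects the restricted set and intermittent testing together.

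**The case against.** The strongest reply is that the entry clause does little harm by itself. For an FVC-only rate or hazard, keeping untested patients and censoring them at index gives the same estimate as leaving them out (step 3). This stands. The distortion comes mainly from progression that nobody observed before death, and a wider set alone does not cure it. The entry clause does matter for cumulative incidence or a composite, where an untested death must be counted.

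A reader might infer that the plan builds in immortal time that favours oxygen. The documents do not support that. The same rule applies from index to first repeat FVC in both cohorts, and last-FVC censoring has the same feature. A bias needs mortality or testing to differ between cohorts, and the documents give no rates from which to fix its direction or size.

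A reader might also infer that the deaths are lost to the study, or that no rule exists anywhere. All-cause mortality is a separate primary outcome, so the deaths are lost only from progression. Section 7.2.3 cites a section 7.6.2.2 that is not in the public text, and a rule for censoring, missing FVC or competing deaths may be there. The definition in 7.3.3.1 would still restrict the set and need reconciling with it.

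Loss of the partner is one of two readings, since the text says patients or matched pairs.

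**Conclusion.** The point holds in a limited form. As written, a primary outcome is confined to those with a post-index measurement, and no visible text handles those who die, leave or go untested first. Under the assumed rates this removes 19–46% of patients. If both members must be retained under common follow-up, about 50–61% of pairs remain with a 6-month mean gap and 23–36% with a 12-month gap. With a mortality hazard ratio of 1.5 and no true progression effect, the ratio in the both-values set is about 0.89–0.97, which flatters the cohort with more deaths. With equal mortality and testing it is about 1. The true size and direction cannot be derived from the documents.

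This should be fixed, but it does not invalidate the plan. Confidence is medium, because the Aim 2 analysis section is not visible and all rates are assumed.

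**What to change.** In section 7.3.3.1:
1. Define the progression set at index: all matched patients with a pre-index FVC and EHR data, whether or not a follow-up FVC exists.
2. Handle death explicitly. Report the cumulative incidence of FVC progression with death as a competing event. Also report progression-or-death (first qualifying FVC decline or death from any cause) with the components shown separately. State the censoring date for patients with neither event.
3. Report, by cohort, the share without a repeat FVC and the reason: died, disenrolled, or enrolled but untested.
4. Keep the set with both FVC values as a descriptive table only.
5. Cross-reference any rule in the Aim 2 analysis section and reconcile it with this definition.

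The cost is revised wording and one re-specified analysis. Death dates and all valid PFT results are already to be captured. The drawback is that the composite mixes FVC decline with death, which is also a primary outcome in its own right, so it cannot be read without its components.

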7.2.3 Study population: Aim 2 [REDACTED]

The analysis for Aim 2 and Further Aim will include patients identified for Aim 1 in Section 7.2.2 who meet the following additional selection criteria. Final oxygen therapy cohorts will be determined during the propensity score matching (PSM) procedure outlined in Section 7.6.2.2.

- **Oxygen therapy cohort**

- ILD patients with ≥ 1 medical claim for oxygen therapy after fibrosing ILD diagnosis. The ***index date*** will be defined as the first date of a claim for oxygen therapy.

- **No oxygen therapy cohort**
 - Matched to a patient in the oxygen therapy cohort. The **index date** will be assigned as a date that is eligible to set an index date (i.e., similar to the matched oxygen therapy patient in time from the fibrosing ILD diagnosis date to the index date, and during the same continuous enrollment period as the fibrosing ILD diagnosis date).

NOTE: Following review of results from Aim 1, the study team will determine whether criteria for Aim 2 and Further Aim require revision.

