7.3.3.2 Secondary Outcomes

- **Hypoxemia**—Sample size permitting, hypoxemia (i.e., oxygen saturation [SpO₂] <90%) will be captured as available in the database using specific ICD-10-CM codes or EHR data among the subset of patients with both claims and EHR in the Market Clarity database. Time to hypoxemia will be reported as time between index date and first evidence of hypoxemia.
- **Respiratory deterioration/Acute exacerbations**—An acute exacerbation of fibrosing ILD has been defined clinically as an unexplained worsening or development of dyspnea within 30 days in combination with a high-resolution CT indicating interstitial pneumonia, and excluding pulmonary infection, left heart failure, pulmonary embolism or other identifiable causes of acute lung injury.⁹ Based on these clinical criteria, acute exacerbations will be defined as follows:
 - ≥1 claim with procedure code for CT scan, and
 - Evidence of dyspnea, as defined by ICD-10-CM codes or EHR data in the integrated database, within 30 days prior to date of CT scan, and
 - No claims with diagnosis for pulmonary infection, left heart failure, pulmonary embolism, or other identifiable causes of acute lung injury within 30 days prior to date of CT scan.

The time to first exacerbation and population annualized counts of exacerbations (sum of all exacerbations for all individuals / sum of follow-up time [person years] for all individuals) will be described. Exacerbations occurring within 14 days of each other will be considered a single exacerbation episode. The start date of the exacerbation episode will be the service date of the first event (i.e., dyspnea or CT scan). The end date of the exacerbation episode will be defined as the last observed exacerbation event date (or discharge date if event occurs during an inpatient stay) + 14 days. Exacerbation episodes that include an inpatient stay will also be reported separately as exacerbations involving a hospitalization.

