7.8 LIMITATIONS OF THE RESEARCH METHODS

This study should be considered in the context of its limitations. First, identification of patients with newly diagnosed fibrosing ILD will rely on application of a claims-based algorithm. Presence of a diagnosis code does not necessarily indicate presence of disease; however, to limit misidentification of ILD patients, a confirmatory diagnosis will be required. Further, patients without ILD diagnosis in the 12-month baseline will be considered newly diagnosed. However, it is possible that patients with prevalent ILD who have not sought frequent care for their condition may be misclassified as newly diagnosed ILD patients.

Second, this study will utilize both claims and EHR data available in Optum's Market Clarity Integrated Claims + Clinical database to capture ILD symptoms, pulmonary function testing results, and hypoxemia. EHR data will be available for only a subset of the identified population; for remaining patients, these values will rely on information available in claims. Further, the analysis will rely on the availability of valid values (e.g., laboratory results) in the EHR data.

Third, all ILD patients included in this study were enrolled in a health plan (i.e., commercial, Medicare, or Medicaid) during the study period; thus, findings from this study may not be applicable to uninsured populations and patients with health plans not represented in the database.

Fourth, this study will minimize bias by utilizing propensity score matching on baseline variables (oxygen therapy versus no oxygen therapy cohorts) to examine outcomes of interest. Employing matching will enable a comparison of outcomes among patients who were similar on pre-ILD baseline characteristics. However, residual and/or unobserved confounding cannot be ruled out.

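### The Aim 2 progression outcome is an unsigned 10% FVC change to a single follow-up value; if that is the latest value, as the section suggests, earlier crossings are dated late or missed

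*Combined protocol and SAP*

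**What the plan says.** The abstract heads its Aim 2 list with this outcome: "Primary Outcomes: Time to disease progression; time to all-cause mortality". Section 7.3.3.1 gives the definition. Pulmonary function results are taken as they occur in the database, and "All valid result values will be captured". For the pre-index period, "values closest to the index date will be reported for the pre-index baseline period". For follow-up, "the latest values prior to the end of follow-up will be reported for the Aim 2 follow-up period". Among patients or matched pairs with FVC in both periods, "disease progression will be defined as a 10% relative change between the pre-index value and the follow-up value". The section then says that the time to progression is reported and that, in addition, the intervals from pre-index FVC to index and from index to the follow-up FVC are reported. It does not say which date is the event date.

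Other outcomes are dated explicitly. For example, "Time to hypoxemia will be reported as time between index date and first evidence of hypoxemia". Mortality has a stated start and end, and time to sustained oxygen use (Section 7.3.1.1) runs to the earliest qualifying date.

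**The concern.** A time-to-event variable needs an event rule and an event date. This rule has no sign, so a rise in FVC satisfies it as written. It compares two single values, and the section identifies the follow-up one only as the latest. A programmer working from this text could reasonably compare the last FVC with the pre-index FVC and date the event at the last test. For a patient tested several times, the recorded time would then reflect when testing or follow-up stopped, not when FVC fell. Someone whose FVC fell below the threshold and later recovered would have no event. Another programmer, noting that all valid values are captured, could use the first crossing. The two would obtain different events and different times for a primary outcome.

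**Working it through.** **There is no plan figure to reproduce.** The documents give no event rate, FVC slope, FVC variability or testing frequency for this outcome.

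**Step 1: worked examples.** Relative change = (follow-up − pre-index) / pre-index. The FVC values are invented, with a pre-index FVC of 3.00 L.

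| Follow-up FVC | Relative change | First decline ≥10% | Latest-value rule |
|---|---|---|---|
| 2.65, 2.60, 2.50 L at days 90, 180, 360 | −11.7%, −13.3%, −16.7% | day 90 | day 360 (360 − 90 = 270 days late) |
| 2.65, 2.75 L at days 90, 360 | −11.7%, −8.3% | day 90 | no event |
| 2.65 L at day 180 | −11.7% | day 180 | day 180 |
| 3.40 L | +13.3% | no event | meets an unsigned 10% change |

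**Step 2: illustrative simulation.** Every input is an assumption. Individual slopes are linear, with mean −3, −5 or −8% per year and SD 3 or 6% per year. Test error is multiplicative normal with CV 3 or 5%, on both pre-index and follow-up values. Tests are every 6 or 12 months. This gives 3 × 2 × 2 × 2 = 24 scenarios, and the event is a decline of at least 10%.

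- Late = last-value events with an earlier crossing / all last-value events.
- Delay = last test date − first crossing date, averaged over all last-value events.
- Missed = ever crossed but not past the threshold at the last test / ever crossed.

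The base case is −5% per year, SD 6, CV 5%, 6-monthly tests.

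| Follow-up FVCs | Late: base (range) | Mean delay, months: base (range) | Missed: base (range) |
|---|---|---|---|
| 1 | 0 | 0 | 0 |
| 2 | 35% (13–58%) | 2.1 (0.8–7.0) | 15% (0.7–26%) |
| 3 | 63% (34–88%) | 5.5 (2.5–16.7) | 16% (0.7–30%) |
| 4 | about 80% (56–96%) | 9.8 (5.3–27.4) | 14% (0.5–28%) |

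A rerun agreed within simulation error. The longest delays come from annual tests over three or four years. Data end in June 2022, so four years of follow-up is possible only for patients indexed by about mid-2018.

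**Step 3: how much of the missed share is noise.** In the base case only 14%, 25% and 28% of missed patients (two, three and four tests) had an error-free decline of 10% or more. Among declines seen at two consecutive tests, the last value misses 3.5% with three tests and 3.4% with four.

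**Step 4: is late dating the larger effect?** The late and missed shares above have different denominators. With ever-crossers as the common denominator and 3-monthly tests, missed crossings exceed late ones in 10 of 12 scenarios with two tests, 5 of 12 with three and 3 of 12 with four. Neither effect dominates generally.

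**Step 5: what first crossing costs.** For a stable patient with a single test, the false-crossing probability is Φ(−10 / (CV × √1.81)), where 1.81 = 1 + 0.9². At CV 5% this is Φ(−1.49) = 6.9%; at CV 3% it is Φ(−2.48) = 0.7%.

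| Stable patient, follow-up tests | 1 | 2 | 3 | 4 |
|---|---|---|---|---|
| First crossing, CV 5% | 6.9% | 12.0% | 16.2% | 19.7% |
| First crossing, CV 3% | 0.7% | 1.3% | 1.8% | 2.4% |
| Two consecutive, CV 5% | – | 1.7% | 2.7% | 3.7% |
| Two consecutive, CV 3% | – | 0.06% | 0.11% | 0.15% |

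With base-case slopes and one year of follow-up, going from one to four tests raises the first-crossing event probability from 29% to 42%. Under the last-value rule it stays at 29%.

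**The case against.** The strongest objection is that the public text is incomplete. Section 7.2.3 refers to a matching "procedure outlined in Section 7.6.2.2", but the public text passes from 7.6.1.3 to 7.7. Aim 1's censoring rule stands in its analysis section, so an event-date or censoring rule for Aim 2 may stand in its own. This holds. A reader might infer that the plan as a whole has no event-date rule, and the documents do not support that.

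Second, the sentence on latest values covers all lung function measures and may be descriptive only. Because all valid values are captured, first crossing is not excluded. The separately listed interval from index to follow-up FVC would also repeat the time to progression for progressors if both ended at the last test. This weakens certainty about intent. But that sentence again refers to one follow-up result, and if the latest value is not meant, the section names no follow-up value for the event.

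Third, decline is plainly what progression means, and the choice between more than 10% and at least 10% should affect few patients. That is fair: the missing sign is a drafting error to correct, not evidence that rises are meant to count. The substance lies in which value triggers the event and when.

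Fourth, first crossing makes detection depend on test count. Section 7.3 gives matched pairs equal follow-up, but that does not equalise testing. This is a real cost to the cohort comparison and belongs in the remedy.

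**Conclusion.** The point holds for the outcome definition in Section 7.3.3.1. Followed literally, it counts a 10% rise as progression. With two or more follow-up FVCs, it dates earlier crossings at the last test or misses them. With one follow-up FVC there is no difference. It should be fixed because it affects a primary outcome and the correction is cheap.

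The size is illustrative: every slope, error and test interval is assumed. The number of patients with repeat FVCs is unknown, since "EHR data will be available for only a subset of the identified population" and results are taken only as available. The missing sign and inequality are certain, as is the absence of an event date from this section. That the latest value is the intended trigger is likely but not certain.

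A reader might infer two further things that are not supported. One is that late dating matters more than missed events; the order changes with test spacing, and most missed crossings in the base case are test noise. The other is that the oxygen comparison is biased; nothing in the documents shows that the rule acts differently in the two cohorts.

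**What to change.** Define progression as the first follow-up FVC with a relative decline of at least 10% from the pre-index value closest to index, and date the event at that test. Keep the change to the last value as a descriptive summary. Align the wording with the Aim 2 analysis section, including how patients without the event are censored and how death is handled.

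Add two sensitivity analyses. One requires the decline at two consecutive follow-up FVCs, with a statement that patients with one follow-up FVC cannot meet it. The other uses the last-value rule. Report the number and timing of follow-up FVCs by cohort, including patients with none, so that differential testing can be seen; this reporting does not correct for it.

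The cost is wording and programming, since the values are already captured. The statistical price is more test noise and an event probability that rises with the number of tests, so unequal testing between cohorts could distort the comparison. The sensitivity analyses and the testing report are there to expose that.
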